# 5.6 Dose Modification

Participants will be asked to contact the study team when experiencing a possibly related adverse event. Section 11.1.3.1 describes the assessment of the severity of an adverse event. Briefly, adverse events (except female genital AEs) will be assessed according to the grade associated with the CTCAE term. Female genital AEs will be assessed according to the NIAID DAIDS Female Genital Grading Table (FGGT) (Appendix B), rather than using CTCAE.

For a Grade 1 toxicity of any genital lesion(s) (blisters, ulcerations, or pustules), that is possibly, probably, or definitely related to the study medication, the participant will not receive applications of the study drug until the toxicity has resolved. No dose modification will be made for other Grade 1 adverse events.

For Grade 2 adverse events definitely, probably or possibly related to study agent persisting until the next scheduled agent application, the next application(s) will be omitted until toxicity is resolved to Grade 1 or less.

Participants with Grade 3 or 4 events that are definitely, probably or possibly related to the study agent will receive no further doses and be followed for resolution of adverse events. If appropriate, they should remain on-study and undergo the post-intervention biopsy.

For adverse events not considered related to study agent persisting until the next agent application, the scheduled agent application may be continued or omitted at the discretion of the study physician.

# 5.7 Adherence/Compliance

5.7.1 Participants will be considered compliant if they have applied/received  $\geq 80\%$  of the assigned number of applications.

5.7.2 The compliance will be assessed by the number of applications based on the study calendar and provider applications. The information will be further confirmed by remaining weight of the returned 5-FU cream.

# 6. PHARMACEUTICAL INFORMATION

# 6.1 5-Fluoruracil and Imiquimod

5% 5-FU cream will be acquired from Valeant Pharmaceuticals or Spear Dermatology and will be ordered by the UNC Outpatient Pharmacy and distributed by Investigational Drug Services (IDS). Every effort will be made to acquire the agent from the same supplier throughout the study. The 5-FU will be supplied to participants in the commercially available tube with vaginal applicators. Participants will be taught how to remove the 5-FU cream from the tube to fill the applicator to the 2 gram mark with the cream prior to each self-application. This method of application has been chosen in order to preserve the shelf-life of the commercially available 5-FU cream.

Commercially available imiquimod cream 5% (trade name Aldara) will be acquired from a commercial source (e.g., Fougera, Glenmark, Perrigo) and will be ordered by the UNC Outpatient Pharmacy and distributed by Investigational Drug Services (IDS). Every effort will be made to acquire the agent from the same supplier throughout the study.

# 6.2 Reported Adverse Events and Potential Risks

5-FU: Participants may have side effects from the 5-FU medication. Mild side effects include symptoms, such as burning, redness, or vaginal discharge. Serious side effects include pain, bleeding or vaginal ulcers. This treatment (5% 5-FU once every 2 weeks) has been previously studied in other women and 2% of women (1 out 50) reported mild side effects related to the cream. Our research team assessed women undergoing the same treatment regimen and 48% reported some genital side effect (e.g. burning, irritation, spotting). However, none reported that these side effects interfered with usual

activities, and 83% reported that they had a good experience using the cream. No women reported serious side effects.

Because systemic 5-FU is listed as Federal Drug Administration (FDA) Category X, participants should not be pregnant, and should not become pregnant or breast-feed while using the 5-FU cream because the drug in this study could be teratogenic. To minimize this risk, women will be required to use 2 forms of birth control while consuming the study drug if they are using a short acting form of birth control, such as hormonal oral, transdermal, intravaginal or injectable contraception. Condoms will still be recommended for women who are using long acting forms of contraception or have had a tubal ligation to prevent acquisition of a sexually transmitted infection. Use of condoms will also minimize risk of irritation to a sexual partner. We completed a randomized-controlled trial in women ages 18-29 years and reported no pregnancies during use of the 5-FU study drug using these parameters. Participants will be advised to wash hand thoroughly after use of the cream and bring any unused medications back to study team at the subsequent study visit.

**Imiquimod:** Imiquimod is FDA approved for treatment of external genitalia and perineal warts, condyloma acuminate as well as actinic keratosis and primary superficial basal cell carcinoma in immunocompetent adults.  Imiquimod may induce both local and systemic side effects as has been noted in prior studies. A previous trial of women with high-grade squamous intraepithelial lesions reported women having both local and systemic side effects using self-administered imiquimod therapy intravaginally once a week for 2 weeks, twice a week for 2 weeks and then 3 times a week for 12 weeks (total 16 week therapy, total 42 doses). Mild local side effects (vulvar pain or pruritus) were reported in 92% of participants. Flu-like symptoms and fatigue were reported in 97% of imiquimod participants and 34% of placebo participants. Investigators reported findings, such as erythema, edema, erosion, and ulceration during treatment. Severe findings were improved by holding one dose of therapy. Another trial of self-administered imiquimod (twice a week or every other day dosing for up to 12 doses) for women with CIN 1-3 reported the most common side effect as vaginal discharge. Other reported events included vulvar pain, pruritus, erythema, erosion, myalgia and flu-like symptoms; however, no participant discontinued the study due to these side effects.

Our dosing in this trial (one dose every 2 weeks, up to a total of 8 doses) will be much lower than the above noted studies. Therefore, we expect an improved safety profile. Participants will be advised to use nonsteroidal anti-inflammatory drugs (NSAIDs) (or acetaminophen, if not tolerable to NSAIDs) in the event of systemic symptoms which has been shown to be beneficial and not interfere with efficacy of imiquimod.

# 6.3 Availability

5% 5-FU (trade name Efudex, Valeant Pharmaceuticals) and vaginal applicators will be ordered by the UNC Outpatient Pharmacy and distributed by Investigational Drug Services (IDS).

Commercially available imiquimod cream 5% (trade name Aldara) will be acquired from a commercial source (e.g., Fougera, Glenmark, Perrigo) by the UNC IDS. Every effort will be made to acquire the agent from the same supplier throughout the study.

# 6.4 Agent Distribution

The 5-FU cream and imiquimod cream will be sent directly to the UNC IDS from UNC outpatient pharmacy.

UNC IDS will distribute the study agents to the study staff. 5-FU cream will be distributed to the study participants. Imiquimod cream will be applied by the study physician.

# 6.5 Agent Accountability

The Investigator, or a responsible party designated by the Investigator, must maintain a careful record of the inventory and disposition of all agents received from DCP using the NCI Drug Accountability Record Form (DARF). The Investigator is required to maintain adequate records of receipt, dispensing and final disposition of study agent. This responsibility has been delegated to [name], MPH and the UNC Investigational Drug Service. Include on receipt record from

whom the agent was received and to whom study agent was shipped, date, quantity and batch or lot number. On dispensing record, note quantities and dates study agent was dispensed to and returned by each participant.

# 6.6 Packaging and Labeling

5-FU will be packaged by Valeant Pharmaceuticals or Spear Dermatology. It will be ordered by the UNC Outpatient Pharmacy and stored at the UNC Investigational Drug Service.

Commercially available imiquimod cream 5% will be packaged by the supplier (e.g., Fougera, Glenmark, Perrigo), ordered by the UNC Outpatient Pharmacy and stored at the UNC Investigational Drug Service. Every effort will be made to acquire the agent from the same supplier throughout the study.

# 6.7 Storage

Medications will be stored at room temperature (between 59°F and 86°F) at the UNC IDS. Participants will be instructed to store the agent at room temperature away from the reach of other individuals.

# 6.8 Registration/Randomization

Participants will be considered registered on the date they sign the approved informed consent document with a member of the study staff. A participant identification number (PID) will be assigned by the coordinator from a predetermined list once the subject has been consented. This study does not involve randomization.

# 6.9 Blinding and Unblinding Methods

Not applicable

# 6.10 Agent Destruction/Disposal

The UNC IDS will receive all unused study agents for disposal according to the institutional standards.

# 7. CLINICAL EVALUATIONS AND PROCEDURES

# 7.1 Schedule of Events

Evaluation/ Procedure	Screening/ Consenting Visit	Baseline Visit	Self- Application of 5-FU Wks 1, 3, 5, 7 	Imiquimod Application Visits Wks 2,4,6 	Wk 8 Imiquimod Application Visit 	Self- Application of 5-FU Wks 9, 11, 13, 155	Imiquimod Application Visits - Wks 10, 12, 14 	Wk 16 Imiquimod Application Visit 	End of Study Visit 7,13
						OPTION	AL EXTENSION	PHASE	
InformedConsent	X								
Assess Eligibility; Pathology Review 	Х								
Medical History	X								
Vitals (height  , weight, temp, BP, heart rate)	X 	x		х	х		х	х	x
Karnofsky performance status	х								
Blood for CBC-diff, CMP 	х				х			х	х
Urinalysis	Х								Х
Tobacco		х							x
Alcohol Assessment		v							v
Blood for HIV test	x	Λ							 
Urine for Chlamydia, Gonorrhea NAAT	x								
Urine pregnancy test 	х	х	х	х	х	Х	х	х	х
Colposcopy with digital image		х		х	х		Х	х	х
Cericovaginal lavage, swab of the cervix, swab of the vagina, and cervical brushing for research endpoints		x			X 				x
Cervical cells for Pap smear and HR- HPV									x
Blood and urine for exploratory endpoints		х			X 				x
LEEP or Cone biopsy or Colposcopy- directed biopsy 									x
Concomitant Medications	х	х	х	х	х	х	Х	х	х
Dispense Study		х			X 				
Self administered 5- FU			x			х			
Provider applied				x	x		x	x	
imiquimod				~			~	A	
Collect Study Agent Review Study				x	X X			x	
Calendar				Δ	~			~	v
Participant Survey 									X

						- )		,
Adverse Events	Х	Х	Х	Х	Х	Х	Х	Х
T elephone/email Contact 		Х			Х			
Collection of results								
from additional tests/procedures 								

Height required at Visit 1 only.

 CMP includes serum glucose, urea nitrogen, creatinine, sodium, potassium, chloride, bicarbonate, total protein, albumin, calcium, alkaline phosphatase, ALT, AST, total bilirubin.

 Biopsy confirmed high grade cervical squamous intraepithelial lesions (i.e., CIN3 lesions and CIN2 lesions diagnosis confirmed by positive p16 immunohistochemistry staining) within 12 weeks prior to Baseline Visit.

 Urine pregnancy test will be done at each visit. Participants will be provided with home pregnancy tests and will be instructed to use them prior to each self-application.

 Self-administered 5-FU and provider-administered imiquimod visits will be scheduled on alternating weeks. Agent applications will be delayed during menstrual cycles or omitted for occurrence of study related  $\geq$  grade 2 adverse events. No dose will be applied any sooner than 7 days apart even in the setting of dose delay.

 Following the first 8 applications of study agent, participant will be offered option to continue agent intervention for extension phase for an additional 8 weeks.

 End of Study Visit to occur 4-6 weeks after the last agent application unless encountering scheduling difficulty.

 Contact via phone call, text or email will be used to remind participants to use the study medication, to answer questions participants may have and to review AEs and concomitant medications. Participants will also be reminded to perform pregnancy testing prior to using the study medication, to avoid sexual activity for at least 48 hours after each application of study medication, and to use two forms of birth control including condoms and one other form of contraception when participanting in sexual activity. Prior to study visits, participants will be reminded to bring unused applicators/agents, symptom diary and study calendar to the study visits.

 When encountering scheduling difficulties, all efforts will be made to ensure that the visit date does not deviate for more than 5 business days of the specified timeframe.

 If not done at the End of Study Visit, the procedure will be scheduled within 2 weeks of the End of Study Visit, when feasible.

 The study team will collect results from the follow-up cervical exams/procedures/tests performed within 14 months after the End of Study Visit from the medical records for all participants.

 Cericovaginal lavage for collection of specimens for research endpoints and blood and urine for exploratory endpoints will only be collected at Visit 8 if participant opts to extend treatment for an additional 8 weeks.

 Participants who initiate study agent but terminate prior to study completion should return to the clinic for End of Study procedures.

 Participant Survey is optional. Participants who completed participation in the study and were not given the opportunity to complete the survey at that time may do so by telephone, mail or email once verbal consent has been obtained.

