#### **▼** Regular contact

Alternating weekly reminder of 5-flurouracil application and for AE and compliance evaluation

T

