Four to six weeks after 8 (or 16) applications of agent (or 4-6 weeks after the last agent application, if off agent before completing the 8 or 16 week cycle), participants will return for an End of Study Visit. They will be assessed for weight, vital signs, concomitant medications, review symptom diary and study calendar with study staff. Paricipants will complete tobacco and alcohol assessment forms and will be given the option to complete a survey about their experiences while participating in the study. Participants who completed participation in the study and were not given the opportunity to complete the survey at that time may do so by telephone, mail or email once verbal consent has been obtained. They will undergo blood and urine collection for future research. In addition, a blood sample will be collected for CBC with diff and CMP and urine will be collected for a urinalysis and urine pregnancy test. They will undergo a colposcopic examination with digital imaging of the cervix. Cervical specimens will be collected for research endpoints and future research. Additional cervical cells will be collected and sent to the institutional pathology lab for Pap smear and HR-HPV testing. Participants will undergo a LEEP or Cold Knife Cone procedure at this time. If participants decline LEEP or are young women with CIN 2 whose standard of care recommendation had been to observe disease for 6 months, then participants will be given the option to first undergo colposcopy-directed biopsy to assess for residual disease. If subjects opt to have colposcopy-directed biopsy first, then subjects will undergo a minimum of 2 cervical biopsies (one will be at the site of previously noted disease, second will be an endocervical curettage) for histopathological confirmation to verify no microscopic disease. If there is histologic confirmation of residual high-grade squamous intraepithelial lesions or cytologic evidence of ASC-H/HSIL, participants will undergo a LEEP or cone biopsy at future clinical visit according to current clinical care recommendations. If they have evidence of regression (i.e., < CIN2 on histology or cytologic evidence of LSIL/ASC-US/NILM), participants will be recommended to return 6 months later to repeat colposcopic examination with Pap smear and HR-HPV testing (to be performed as the standard of care).

Digital photos will be evaluated for repeat assessment and lesion measurement by a board-certified Gynecologist or Gynecologic Oncologist.

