Participants will self-apply 5-FU intravaginally on weeks 1, 3, 5 and 7. They will be contacted via phone call, text or email to remind them to use the 5-FU, to answer questions participants may have and to review AEs and concomitant medications. Participants will also be reminded to perform pregnancy testing prior to each time they use the study medication, to avoid sexual activity for at least 48 hours after each application of study medication, and to use two forms of birth control including condoms and one other form of contraception when participating in sexual activity. Agent application will be delayed until the end of menstrual cycle if application date occurs during menses. No dose will be applied any sooner than 7 days apart even in the setting of dose delay. Participants will record study agent applications on study calendar. If a safety concern is identified during the regular contact, participants will be asked to come in for an interim clinic exam.

Participants will return to the clinic every other week (weeks 2, 4, 6 and 8) to assess safety and compliance and for provider applications of imiquimod. Prior to study visits, participants will be reminded to bring unused applicators, tube of 5-FU, symptom diary and study calendar to the study visits. Visits may be delayed due to menstrual cycle. No dose will be applied any sooner than 7 days apart even in the setting of dose delay. At each of these interim visits, participants will be assessed for weight, vital signs, concomitant medications, review of symptom diary and study calendar with study staff, and undergo a urine pregnancy test. The tube of 5-FU cream will be weighed at each visit to check compliance. Participants will undergo a colposcopic examination with digital imaging of the cervix and examination of genital tissues

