# 8. CRITERIA FOR EVALUATION AND ENDPOINT DEFINITION

# 8.1 Primary Endpoint

The primary endpoint is feasibility of a combination agent intervention (once-weekly self-administered intravaginal 5-FU alternating with once-weekly provider-administered imiquimod) in women with biopsy confirmed high grade cervical squamous intraepithelial lesions (i.e., CIN3 lesions and CIN2 lesions diagnosis confirmed by positive p16 immunohistochemistry staining).

Feasiblity is evaluated based on safety and tolerability of the study intervention. For safety, we will assess the number of participants experiencing the dose limiting toxicity (DLT). DLT is defined as Grade 2 or greater toxicity (or Grade 1 toxicity of any genital lesion (blisters, ulcerations, or pustules)) that is possibly, probably, or definitely related and lasts for more than 5 days. For tolerability, we will assess the number of participants who are not able to apply at least 50% of the treatment due to DLT.

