# 13.5 Secondary Objectives, Endpoints, Analysis Plans

The secondary objectives include describing the response (composite endpoint based on histologic regression and clearance of HR-HPV) to intravaginal 5-FU and imiquimod and type specific HR-HPV clearance and measuring changes in the expression of biomarkers of local immune activation (including IFN- $\alpha$ 2, IFN-Y, IL-10, IL-12, IL-1 $\alpha$ , -1 $\beta$ , -6, -8, MIP-1 $\alpha$ , TNF) after treatment with self-administered intravaginal use of 5-FU and imiquimod. The response and type-specific HR-HPV clearance will be reported along with their 95% confidence intervals. For each biomarker, the mean change and the associated standard deviation will be reported. Analyses will be performed on all participants who provide post-intervention specimens for endpoint evaluation. Assume an attrition rate of 15% (for completing intervention and providing post-intervention specimens). There will be at least10 participants available for the secondary analyses. Based on a sample size of 10, it allows us to construct a 95% confidence interval for the overall response and clearance rate, respectively, with a width  $\leq 0.72$ . It also allows us to construct a 95% confidence interval for the overall change in expression of each biomarker with a distance from the mean change  $\leq 0.72$  standard deviations. With an anticipated attrition rate of 15%, we will try to reduce the fraction of participants with missing outcomes as much as possible. Also, multiple imputation techniques will be used to handle missing data. Similar to the primary endpoints, each of the secondary endpoints will be also reported by whether or not the participants continue to the expansion phase.

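### No adverse-event contact or examination is scheduled between a woman's last application and End of Study 4–6 weeks later, so DLTs that resolve in that gap rest on diary, self-report and recall

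*Combined protocol and SAP*

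**What the plan says.** - **Remote contacts follow the 5-FU weeks.** The schema describes them as "Alternating weekly reminder of 5-flurouracil application and for AE and compliance evaluation". Section 7.3, after listing the 5-FU weeks, says "They will be contacted via phone call, text or email to remind them to use the 5-FU, to answer questions participants may have and to", and the sentence goes on to the review of adverse events and concomitant medication. Footnote 8 to the Section 7.1 table gives the same content.
- **Examinations follow the imiquimod visits.** Section 7.3: "Participants will return to the clinic every other week (weeks 2, 4, 6 and 8) to assess safety and compliance". Colposcopy is part of these visits. The extension repeats the same timetable.
- **After the last dose.** Section 7.1, footnote 7: "End of Study Visit to occur 4-6 weeks after the last agent application unless encountering scheduling difficulty". Footnote 9 adds a tolerance: "all efforts will be made to ensure that the visit date does not deviate for more than 5 business days of the specified timeframe". Section 3 applies the same interval to early stoppers: "or 4-6 weeks after the last agent application, if off agent before completing the 8 or 16 week cycle".
- **Primary endpoint.** Section 8.1 counts women with a DLT, meaning toxicity of Grade 2 or higher, or a Grade 1 genital blister, ulceration or pustule, "that is possibly, probably, or definitely related and lasts for more than 5 days". Section 13.4 stops further development if 33% or more of participants have one.
- **Reporting by continuation.** Section 13.5: "Similar to the primary endpoints, each of the secondary endpoints will be also reported by whether or not the participants continue to the expansion phase".
- **Other capture of adverse events.** Women keep a symptom diary from screening (Sections 3 and 7.2) and are asked to call about possibly related events (Section 5.6). Staff review the diary at End of Study (Section 7.4).

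**The concern.** The DLT count is the primary endpoint and decides go or no-go. A DLT can be over in less than a week. The review interval during treatment, about 7 days, suits that definition; the interval after the last dose, 28 to 42 days, does not. An event that begins and ends in the gap has to be reconstructed from the diary and memory, although attribution, grade and a duration of more than 5 days must all be established for it to count. Any loss runs in one direction, towards fewer DLTs and a go decision, in a study whose own rationale (Section 2.3) is the lack of safety data on combining agents on the cervix.

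There is also a smaller asymmetry. The same week 8 dose is followed by a contact and an examination in women who continue, and by neither in women who do not. Section 13.5 implies that the primary endpoint will be shown by that status.

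**Working it through.** **Step 1. Time to the next scheduled assessment** (Sections 3, 5.1, 7.1, 7.3 and 7.4; menses may lengthen the intervals during treatment).

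| Application | Next adverse-event review | Next examination |
|---|---|---|
| Any 5-FU dose followed by an imiquimod visit | about 7 days | about 7 days |
| Imiquimod, weeks 2, 4, 6 (and 10, 12, 14) | about 7 days (contact) | about 14 days |
| Imiquimod, week 8, continuing | about 7 days (week 9) | about 14 days (week 10) |
| Imiquimod, week 8, not continuing | 28–42 days | 28–42 days |
| Imiquimod, week 16 | 28–42 days | 28–42 days |
| Last dose, early stoppers | 28–42 days | 28–42 days |

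Five business days are one calendar week, so the outer limit is 42 + 7 = 49 days. The week 8 and week 16 examinations take place at the visit where the dose is given, so they cannot show its effects.

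**Step 2. Events that fit in the gap.** A DLT lasts at least 6 days. With the earliest End of Study at day 28, an event lasting 6 to about 27 days can start and resolve with no scheduled contact or examination. A later visit widens the window.

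**Step 3. The plan's own figures.** With X binomial(12, p) and no-go at X ≥ 4 (4/12 = 33.3%), the chance of no-go is 1 − Σ C(12, x) pˣ (1 − p)¹²⁻ˣ for x = 0 to 3. At p = 0.30 this is 1 − (0.0138 + 0.0712 + 0.1678 + 0.2397) = 0.507, the stated 50.7%. The other entries also reproduce: 2.6% at p = 0.10, 20.5% at 0.20, and 0.2% at 0.05 against the stated < 1%. No figure in Section 13.4 is disputed.

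**Step 4. One event.** 4/12 = 33.3% is no-go; 3/12 = 25% is not. With 13 or 14 treated the boundary is 5 against 4 (5/13 = 38.5%, 4/13 = 30.8%; 5/14 = 35.7%, 4/14 = 28.6%), so one event can still change the result.

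**Step 5. Illustration under an assumption.** Let L be the share of women with a DLT whose only DLT follows the last dose and is never established. L is not in the documents; 12.5% simply mirrors one application in eight. Replacing p by p(1 − L), with all 12 women affected:

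| True DLT rate | L = 0 | L = 6.25% | L = 12.5% | L = 25% |
|---|---|---|---|---|
| 30% | 50.7% | 44.9% | 39.0% | 27.6% |
| 40% | 77.5% | 71.8% | 65.3% | 50.7% |

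For example, 0.30 × (1 − 0.125) = 0.2625, which gives 39.0%. If only 6 of the 12 women are affected (also assumed) and L = 12.5%, the chance of no-go is 44.9% at a true 30% and 71.8% at 40%.

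**The case against.** The strongest reply is that adverse-event capture does not stop at the last dose. The diary is kept at the time, women are asked to call, and staff review diary and adverse events at End of Study, where colposcopy is also done. Women with related Grade 3 or 4 events are followed to resolution (Section 5.6), and Section 8.3 promises continued follow-up where possible for those off agent. A symptomatic DLT can therefore often be recovered with its dates. This stands: the weakness is delayed and retrospective ascertainment. A reader might infer that such DLTs go wholly unrecorded; the documents do not support that.

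A reader might also infer that only women who stop at week 8 are affected. Sections 3 and 7.4 show otherwise, because the same interval follows week 16 and early stopping. What differs by continuation status is only the follow-up of the week 8 dose. That difference should not be pressed far: Section 13.4 specifies no split, no formal comparison is planned, and the groups are self-selected and differ in exposure.

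Third, several Grade 2 signs in Appendix B, such as extent of erythema, cervical friability and clinician-observed discharge, need an examination, which a telephone call does not provide. That is correct. Examination comes about 14 days after every earlier imiquimod dose as well, so a silent event of 6 to 13 days can already pass unseen. Appendix B also keeps findings seen only by colposcopy out of its lesion grades.

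Finally, because DLTs are counted per woman, a loss requires that her only DLT follow the last dose, resolve early and escape diary, call and recall. The documents give no rate for this, and nothing in them says that toxicity rises with cumulative exposure.

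**Conclusion.** The point holds as a gap in scheduled ascertainment of the primary endpoint. After each woman's last application the first scheduled adverse-event review comes at 28 to 42 days (49 at the outside), against about 7 days after every earlier dose and a DLT threshold of more than 5 days. Events that resolve in between are less reliably dated, graded and counted, and any error favours go.

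The number of DLTs affected cannot be derived. One missed event is enough to cross the boundary, but that shows how fragile a 12-woman rule is and does not show that a miss is likely. The fall in the chance of no-go at a true 30% rate, from 50.7% to between 44.9% and 27.6%, rests entirely on the assumed L and on all 12 women being affected. The plan does not say whether extension-phase DLTs count towards the 33% rule. If they do not, only the last doses of women who do not continue, or who stop early in the initiation phase, bear on the decision. This is an inexpensive improvement worth making; it does not invalidate the design or any stated figure.

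**What to change.** In the Section 7.1 table and in Section 7.4, add one telephone, text or email contact about 1 week after the last application for every woman: week 9 if she does not continue, week 17 after the extension, and one week after the last dose in early stoppers. Use the adverse-event and concomitant-medication review already described in footnote 8, and the interim clinic examination that Section 7.3 already provides when a contact raises a safety concern.

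This restores the contact interval used for earlier doses and gives the week 8 dose a week 9 contact whatever the woman decides. Continuers will still have a week 10 examination that the others lack, and the contact will not detect symptomless, examination-only findings.

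The cost is one contact per woman, at most 14, by existing staff, with no scheduled clinic visit added. The observed DLT rate may come out slightly higher.
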